3. STUDY OBJECTIVES AND ENDPOINTS

3.1. Study Objectives

Primary:

To assess the safety, reactogenicity, and tolerability of the HydroVax-002 YFV vaccine administered intramuscularly in a two-dose series on Days 1 and 29 at a dose of 1 mcg or a dose of 5 mcg

Secondary:

To assess YFV-specific neutralizing antibody responses after a first dose and after a second dose of HydroVax-002 YFV vaccine given at dose levels of 1 mcg and 5 mcg

Exploratory:

To assess long-term YFV-specific neutralizing antibody responses after a second dose of HydroVax-002 YFV vaccine given at dose levels of 1 mcg and 5 mcg

3.2. Endpoints

Primary Outcome Measures:

- Occurrence of all serious adverse events (SAEs) at any time during the study
- Occurrence of all Grade 3 unsolicited adverse events (AEs) from first vaccination through Day 29 after the second vaccination
- Occurrence of all Grade 3 laboratory toxicities from first vaccination through Day 15 after the second vaccination
- Occurrence of solicited local AE and reactogenicity signs and symptoms in the 7 days after each vaccination
- Occurrence of solicited systemic AE and reactogenicity signs and symptoms in the 7 days after each vaccination
- Occurrence of any AE through Day 29 after the second vaccination

Secondary Outcome Measures:

- Percentage of subjects achieving seroconversion ($\geq 1:10$ in plaque reduction neutralizing titer [PRNT₅₀] titer, at Day 29 after first vaccination and at Day 29 after second vaccination
- Geometric mean neutralizing titers at days 15 and 29 after first vaccination and at Days 15, 29, and 57 following second vaccination
- Reverse cumulative distribution curve of neutralizing titers on Days 15 and 29 after first vaccination and at Days 15, 29 and 57 after the second vaccination for each dose group and for all dose groups combined

Exploratory Outcome Measures:

- Geometric mean neutralizing titers at Day 180 following second vaccination
- Reverse cumulative distribution curve of neutralizing titers on Day 180 after the second vaccination for each dose group and for all dose groups combined

3.3. Study Definitions and Derived Variables

Seroconversion is defined as a PRNT₅₀ neutralizing antibody titer of $\geq 1:10$. The limit of detection in the neutralizing assay will be a titer of <10 . For the purposes of determining seroconversion rates and GMT, antibody titers of <10 will be assumed to be 5 (one dilution step below the assay limit value).

For exploratory analysis using the LNI measurement the limit of detection will be defined as 0.70, and seroconversion is defined as an LNI value ≥ 0.70 . For the purposes of determining seroconversion rates and GMT, LNI titers of <0.70 will be set to value of 0.35 (one-half the limit of detection).

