9.4.3 Analysis of Secondary and Exploratory Outcome Measures (Immunogenicity)

Basic descriptive statistics, such as point estimates and 95% confidence intervals, and graphical summaries, such as the reverse cumulative distribution, of seroconversion rates and geometric mean titer (GMT) will be computed by intervention at baseline, 15 and 29 days after the first vaccination, and 15, 29, 57, and 180 days after the second vaccination. YFV-specific neutralizing antibody titers may be measured through a standard plaque reduction neutralizing titer [PRNT₅₀] assay, or utilizing a Log₁₀ Neutralizing Index (LNI) assay [5, 38]. For the purposes of this study, and in line with recent yellow fever vaccine clinical trials [7, 8], antibody titers will be assessed using the PRNT₅₀ assay, and seroconversion will be defined as a PRNT₅₀ neutralizing antibody titer of $\geq 1:10$. The limit of detection in the neutralizing assay will be a titer of <10 . For the purposes of determining seroconversion rates and GMT, antibody titers of <10 will be assumed to be 5 (one dilution step below the assay limit value).

Rates of seroconversion will be summarized by tabulating the frequency of positive responses by treatment group at Day 29 after first vaccination and Day 57 after second vaccination. Response rates for each treatment group will be presented with their corresponding 95% confidence interval estimates at each time point. The relationship between the proportion of responders and dosage will be examined using logistic regression. The distribution of antibody titers will also be graphically summarized using the reverse cumulative frequency distribution of titers for each treatment group.

The PRNT₅₀ titers at days 15 and 29 after first vaccination and at days 15, 29, and 57 following second vaccination will be summarized graphically for each treatment group. The geometric mean titer (GMT) and pair-wise differences of each treatment group will also be presented with 95% confidence intervals. The relationship between GMT and dosage will be examined using standard linear regression methods. Secondary outcome measures include:

- Percentage of subjects achieving seroconversion ($\geq 1:10$ in plaque reduction neutralizing titer [PRNT₅₀] titer) at day 29 after first vaccination and at day 29 after second vaccination.

- Geometric mean neutralizing titers at days 15 and 29 after first vaccination and at days 15, 29, and 57 following second vaccination.

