6.4.2. Full Analysis Population

The full analysis (FA) population will consist of all subjects who received any study product (including control) and for whom immunogenicity endpoint data are available. In the case of mis-randomization subjects will be analyzed according to the study product actually received. Separate populations for each assay and/or dose may be needed if the availability of a sample's data varies across assay or if a subject is only eligible for analyses for one of the doses. For sake of simplicity, immunogenicity tables and figures will use a single "Full Analysis Population" label, however special cases and/or considerations for exclusions from assay- or dose-specific summaries will be provided in footnotes.

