9.2. Secondary and Exploratory Analysis

An alternative approach to assessing neutralizing titers is using a constant amount of serum and serial dilutions of the virus inoculum. This approach is referred to as a log-neutralizing index (LNI) and has been used in the past to assess immunogenicity following vaccination with YFV vaccine candidates. The log neutralizing index (LNI) and associated exact Blaker 95% confidence interval will be presented by treatment group at baseline Days 15 and 29 after the first vaccination and Days 15, 29, 57 and 180 after the second vaccination in both the FA ([Table 30](#)) and PP ([Table 31](#)) populations, as defined in [Section 6.4.2](#). A listing of all LNI results will be provided ([Listing 14](#)). For each study day, the number of subjects in the FA or PP population with available immunogenicity data at the particular study day will be presented and used in calculations. The reverse cumulative distribution of the LNI titer by Study Day and treatment group will also be generated for each vaccination in both the FA and PP populations ([Figure 15](#), [Figure 16](#), [Figure 17](#), and [Figure 18](#)).

The number of subjects seroconverting by either the LNI or PRNT₅₀ measurements will be enumerated in either the FA ([Table 32](#)) or PP ([Table 33](#)) populations.

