	Max Severity Post Baseline	HydroVax-002 YFV -1 mcg	XX	X	X.X	X	X.X	X	X.X	X	X.X
		HydroVax-002 YFV -5 mcg	XX	X	X.X	X	X.X	X	X.X	X	X.X
		Placebo	XX	X	X.X	X	X.X	X	X.X	X	X.X

Repeat for all laboratory parameters...

The "Max Post Baseline" rows indicate the maximum severity experienced by each subject at any time point post baseline, including unscheduled assessments.

N = Number of subjects in the Safety population with available laboratory results.

Implementation note: This table will be repeated for all hematology, blood chemistry and urinalysis parameters.

Table 29: Abnormal Laboratory Results Related to Study Treatment by Parameter, Maximum Severity, Study Day, Treatment Group and Parameter – Any Parameter

Parameter	Time Point	Treatment Group	Mild/ Grade 1			Moderate/ Grade 2		Severe/ Grade 3	
			N	n	%	n	%	n	%
[Parameter 1]	Day 4 Post-Dose 1	HydroVax-002 YFV -1 mcg	XX	x	x.x	x	x.x	x	x.x
		HydroVax-002 YFV -5 mcg	XX	x	x.x	x	x.x	x	x.x
		Placebo	XX	x	x.x	x	x.x	x	x.x
	Day 15 Post-Dose 1	HydroVax-002 YFV -1 mcg	XX	x	x.x	x	x.x	x	x.x
		HydroVax-002 YFV -5 mcg	XX	x	x.x	x	x.x	x	x.x
		Placebo	XX	x	x.x	x	x.x	x	x.x
	Day 29 Post-Dose 1	HydroVax-002 YFV -1 mcg	XX	x	x.x	x	x.x	x	x.x
		HydroVax-002 YFV -5 mcg	XX	x	x.x	x	x.x	x	x.x
		Placebo	XX	x	x.x	x	x.x	x	x.x
	Day 4 Post-Dose 2	HydroVax-002 YFV -1 mcg	XX	x	x.x	x	x.x	x	x.x
		HydroVax-002 YFV -5 mcg	XX	x	x.x	x	x.x	x	x.x
		Placebo	XX	x	x.x	x	x.x	x	x.x
	Day 15 Post-Dose 2	HydroVax-002 YFV -1 mcg	XX	x	x.x	x	x.x	x	x.x
		HydroVax-002 YFV -5 mcg	XX	x	x.x	x	x.x	x	x.x
		Placebo	XX	x	x.x	x	x.x	x	x.x
	Max Severity Post Baseline	HydroVax-002 YFV -1 mcg	XX	x	x.x	x	x.x	x	x.x
		HydroVax-002 YFV -5 mcg	XX	x	x.x	x	x.x	x	x.x
		Placebo	XX	x	x.x	x	x.x	x	x.x

Repeat for all laboratory parameters...

The “Max Post Baseline” rows indicate the maximum severity experienced by each subject at any time point post baseline, including unscheduled assessments.

N = Number of subjects in the Safety population with available laboratory results.

Implementation note: This table will be repeated for all hematology, blood chemistry and urinalysis parameters.

Table 30: PRNT₅₀ Geometric Mean Titer (GMT) and Log Neutralizing Titer Index (LNI) Results with 95% Confidence Intervals by Study Day and Treatment Group, Full Analysis Population

Visit	HydroVax-002 YFV 1 mcg			HydroVax-002 YFV 5 mcg			Placebo		
	N	GMT	95% CI	N	GMT	95% CI	N	GMT	95% CI
PRNT₅₀									
Day 1 (pre-vaccination)	XX	X.XX	X.XX, X.XX	XX	X.XX	X.XX, X.XX	XX	X.XX	X.XX, X.XX

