Table 32: Number of Subjects Seroconverting for LNI Compared to PRNT₅₀ by Dose, Full Analysis Population

		PRNT ₅₀					
Population	Status by LNI	Seroconversion			No Seroconversion		
		N	%	95% CI	N	%	95% CI
Day 29 Post-Dose 1	Seroconversion	x	x.x	x.x, x.x	x	x.x	x.x, x.x
	No Seroconversion	x	x.x	x.x, x.x	x	x.x	x.x, x.x
Day 57 Post-Dose 2	Seroconversion	x	x.x	x.x, x.x	x	x.x	x.x, x.x
	No Seroconversion	x	x.x	x.x, x.x	x	x.x	x.x, x.x

Table 33: Number of Subjects Seroconverting for LNI Compared to PRNT₅₀ by Dose, Per-Protocol Population

		PRNT ₅₀					
Population	Status by LNI	Seroconversion			No Seroconversion		
		N	%	95% CI	N	%	95% CI
Day 29 Post-Dose 1	Seroconversion	X	X.X	X.X, X.X	X	X.X	X.X, X.X
	No Seroconversion	X	X.X	X.X, X.X	X	X.X	X.X, X.X
Day 57 Post-Dose 2	Seroconversion	X	X.X	X.X, X.X	X	X.X	X.X, X.X
	No Seroconversion	X	X.X	X.X, X.X	X	X.X	X.X, X.X

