Figure 11: Reverse Cumulative Distribution of PRNT₅₀ by Study Day, HydroVax-002 YFV 1 mcg, Full Analysis Population

[figure not shown]

Figure 12: Reverse Cumulative Distribution of PRNT₅₀ by Study Day, HydroVax-002 YFV 5 mcg, Full Analysis Population

[figure not shown]

Figure 13: Reverse Cumulative Distribution of PRNT₅₀ by Study Day, HydroVax-002 YFV 1 mcg, Per Protocol Population

[figure not shown]

Figure 14: Reverse Cumulative Distribution of PRNT₅₀ by Study Day, HydroVax-002 YFV 5 mcg, Per Protocol Population

[figure not shown]

Figure 15: Reverse Cumulative Distribution of Log Neutralizing Index (LNI) by Study Day, HydroVax-002 YFV 1 mcg, Full Analysis Population

[figure not shown]

Figure 16: Reverse Cumulative Distribution of Log Neutralizing Index (LNI) by Study Day, HydroVax-002 YFV 5 mcg, Full Analysis Population

[figure not shown]

Figure 17: Reverse Cumulative Distribution of Log Neutralizing Index by Study Day, HydroVax-002 YFV 1 mcg, Per Protocol Population

[figure not shown]

Figure 18: Reverse Cumulative Distribution of Log Neutralizing Index (LNI) by Study Day, HydroVax-002 YFV 5 mcg, Per Protocol Population

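### Seroconversion is defined without a Day 1 condition, so a subject positive on Day 1 who is still at or above the threshold at the analysis visit counts as a converter

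*SAP*

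**What the plan says.** SAP 3.3 states: "Seroconversion is defined as a PRNT₅₀ neutralizing antibody titer of" at least 1:10. The same section sets the exploratory LNI version at 0.70 or above. Protocol 9.4.3 agrees: "seroconversion will be defined as a PRNT₅₀ neutralizing antibody titer of" at least 1:10. The secondary endpoint in Protocol 3 and SAP 3.2 is the percentage meeting that threshold at Day 29 after each dose. None of these places mentions the Day 1 titer, a fold rise, or what to do with a subject already positive on Day 1.

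Protocol 9.4.3 also plans descriptive summaries "of seroconversion rates and geometric mean titer (GMT) will be computed by intervention at baseline, 15 and 29 days after the first vaccination" and at the later visits, and it tabulates the rate as a count of positive responses.

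In the SAP, seroconverters are counted only in Tables 32 and 33. The first is titled "Number of Subjects Seroconverting for LNI Compared to PRNT₅₀ by Dose, Full Analysis Population". SAP 9.2 says that the numbers seroconverting by the two "measurements will be enumerated in either the FA" or the PP population. The shells cross LNI status with PRNT₅₀ status at Day 29 post-dose 1 and Day 57 post-dose 2, and show no treatment-arm columns.

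No analysis population closes the gap. The full analysis population (SAP 6.4.2) is "all subjects who received any study product (including control) and for whom immunogenicity endpoint data are available". The per protocol population (SAP 6.4.3) adds receipt of both doses and no major deviation. The evaluable population in Protocol 9.3 needs a valid pre-vaccination result, but not a negative one. Screening serology (Protocol 8.1.1) covers HIV, hepatitis B and hepatitis C. Earlier flavivirus exposure is excluded by history (Protocol 5.2), for which an interview suffices (Protocol 10.1.9.3).

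**The concern.** The secondary objective is the antibody response to the first and second doses. Conversion is a change from negative to positive, whereas the rule records only a state at one visit. Computing the rate at baseline shows this plainly: nobody can have converted before dose 1, so a nonzero value there can only be seropositivity.

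With 10 subjects per vaccine group and 5 on placebo, one carried-over positive is visible in the result. In a vaccine group it credits the vaccine with antibody that predates it. In placebo, which Protocol 4.2.1 includes partly as a control for the antibody assays, it produces a converter where nothing has changed. The Day 57 results may inform the design of later trials (SAP 2.1).

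**Working it through.** **Plan's own figure.** Neither document gives a precision figure for seroconversion. The one exact bound stated is for safety: 0 events in 10 gives an upper 95% limit of 30.8% (Protocol 9.2.1, SAP 5). The two-sided exact formula gives 1 − 0.025^(1/10) = 0.3085, which agrees. Exact (Clopper-Pearson) 95% intervals are used below. Protocol 9.4.3 names no interval method for these rates.

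**Inputs.** Group sizes are 10, 10 and 5 (SAP 5). Assume that one subject in the arm is positive on Day 1 and still at or above 1:10 at the analysis visit. Let k be the number of true converters among the others.

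**Vaccine group of 10.** The rule as written gives (k+1)/10. With Day 1 negatives as denominator the rate is k/9. The difference is (k+1)/10 − k/9 = (9 − k)/90.

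| k | Day 1 negatives only | As written | Difference |
|---|---|---|---|
| 0 | 0/9 = 0% (0–33.6%) | 1/10 = 10.0% (0.3–44.5%) | +10.0 points |
| 4 | 4/9 = 44.4% (13.7–78.8%) | 5/10 = 50.0% (18.7–81.3%) | +5.6 points |
| 8 | 8/9 = 88.9% (51.8–99.7%) | 9/10 = 90.0% (55.5–99.7%) | +1.1 points |
| 9 | 9/9 = 100% | 10/10 = 100% | 0 |

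**Placebo group of 5.** The difference is (k+1)/5 − k/4 = (4 − k)/20. At k = 0, 0/4 (0–60.2%) becomes 1/5 (0.5–71.6%), or +20.0 points.

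**Choice of denominator.** If the Day 1 positive were kept in the denominator as a non-converter, the difference in a vaccine group would be (k+1)/10 − k/10 = 10.0 points at every k. At k = 4 that is 10.0 points rather than 5.6, so the denominator has to be stated along with the condition.

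**No Day 1 positives.** Both rules give the same numerator and denominator, so the rates are identical.

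**How often.** The documents give no prevalence q of Day 1 positivity among enrolled subjects. For illustration only, the chance of at least one among 25 is 1 − (1 − q)^25: 22.2%, 39.7%, 72.3% and 92.8% at assumed q of 1%, 2%, 5% and 10%. The conclusion does not rest on any of these values.

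**The case against.** The strongest reply is that the defect may never occur. Protocol 5.2 selects for flavivirus-naive subjects: it excludes long stays in three regions, military service, flavivirus vaccination, schooling in nine countries and past yellow fever. This stands, and it limits the likely size.

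A second reply is that the matter is one of naming. The rule is consistent across both documents and can be programmed, the analyses are descriptive and unpowered, and Protocol 9.4.3 says the approach follows recent yellow fever vaccine trials. That supports 1:10 as an assay threshold. It does not say how a Day 1 positive is handled or which denominator applies. Renaming alone would make the label honest, but would leave the trial without a rate of conversion.

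Two stronger readings are tempting, and the documents support neither.

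- A reader might infer that every Day 1 positive is counted as a converter. The titer must also be at or above the threshold at the analysis visit.
- A reader might infer that the Day 57 displays cannot show how many subjects were positive on Day 1. The Day 1 row of Tables 30 and 31 gives N, GMT and a 95% CI. With titers below 10 set to 5 and n = 10, one subject at 1:20 and two at 1:10 both give a GMT of 5.74 (5 × 4^(1/10) = 5 × 2^(2/10)). The interval can still separate them: an ordinary log-scale t interval gives 4.20–7.86 and 4.66–7.08 respectively (the t method is an assumption, since SAP 9.1 names another). Figures 11 to 14, such as "Reverse Cumulative Distribution of PRNT₅₀ by Study Day, HydroVax-002 YFV 5 mcg, Full Analysis Population", run by study day and may include a Day 1 curve for the vaccine groups; the panels are not visible in the posted text. Listing 14 gives every subject's titers at the final analysis.

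These displays may reveal a Day 1 positive, but they do not remove that subject from the count of converters.

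**Conclusion.** The point holds. The stated rule measures seropositivity, and it gives a wrong seroconversion rate whenever a Day 1 positive stays at or above the threshold. For one such subject the excess is at most 10 percentage points in a vaccine group, shrinking to zero as the other nine all convert. It is 20 points in placebo when no other placebo subject is positive. These sizes assume complete data in groups of 10 and 5, and Day 1 negatives as the correct denominator.

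Nothing in the documents shows that such a subject exists. The exclusions make it uncommon, and the frequency cannot be derived. The change is worth making because the rule is wrong for its stated objective and the correction needs no new samples. It is better settled before unblinding than after a Day 1 positive has been seen.

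**What to change.** - **Definition (SAP 3.3; Protocol 3 and 9.4.3).** Seroconversion is a Day 1 PRNT₅₀ titer below 1:10 and a post-dose titer of at least 1:10. The denominator is subjects negative on Day 1 by PRNT₅₀ with a valid result at that visit. Apply the same rule to LNI, using 0.70.
- **Display.** Add a seroconversion table at the endpoint visits, by arm, with the rate, its 95% CI and the number of Day 1 positives.
- **Existing rate.** Keep the threshold rate at every visit, including baseline, and call it seropositivity.
- **Tables 32 and 33.** A subject can be Day 1-negative by one assay and positive by the other, so an added row would not repair these cross-tabulations. Either restrict them to subjects Day 1-negative by both assays, or label them as agreement on seropositivity.
- **Populations.** SAP 6.4.2 does not ask for a Day 1 sample, while Table 2 excludes subjects without pre- and post-baseline draws. Align the two, since the new denominator needs a Day 1 result.

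The cost is wording in both documents, one new table and a decision on Tables 32 and 33. Day 1 PRNT₅₀ is already scheduled (Protocol 8.1.2.1), and SAP 9.2 already plans a baseline LNI summary. The downside is a slightly smaller denominator, for example 9 instead of 10.

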6.6. Missing Data

Missing safety and/or immunogenicity data will not be imputed. No search for outliers will be performed. However, the logarithmic transform will be used as appropriate to improve the distributional properties of the immunogenicity data and reduce the impact of potential outliers.

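### The SAP's wording and table shells imply a geometric mean of LNI, which is already a log10 value, with an interval that is not made for a mean

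*SAP*

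**What the plan says.** - **Scale of LNI.** Protocol 9.4.3 mentions measuring antibody by "utilizing a Log₁₀ Neutralizing Index (LNI) assay", and the protocol's abbreviation list also expands LNI as a log10 index.
- **Limit and substitution.** SAP 3.3 states that "the limit of detection will be defined as 0.70, and seroconversion is defined as an LNI value ≥ 0.70". It then gives the rule for values below the limit: "determining seroconversion rates and GMT, LNI titers of <0.70 will be set to value of 0.35", which it describes as half the limit. The named uses of the substituted values are the seroconversion rate and the GMT.
- **Text on the summary.** SAP 9.2 says: "The log neutralizing index (LNI) and associated exact Blaker 95% confidence interval will be presented by treatment group". It does not say whether the point value is an arithmetic mean, a geometric mean or a median. The parallel sentence for PRNT50 in SAP 9.1 does name a geometric mean titer.
- **Table shells.** Table 30 is titled PRNT50 "Geometric Mean Titer (GMT) and Log Neutralizing Titer Index (LNI) Results with 95% Confidence Intervals by Study Day and Treatment Group, Full Analysis Population". Its only column heads are N, GMT and 95% CI, and they serve both the PRNT50 block and the LNI block. Table 31 (Per Protocol) has the same layout.
- **Log transform.** SAP 6.6 says that "the logarithmic transform will be used as appropriate to improve the distributional properties of the immunogenicity data", and LNI is not exempted.
- **Role.** Protocol 9.4.3 lists LNI under exploratory measures, as an optional analysis for comparison with historical datasets. SAP 3.2 does not list it as an outcome measure.

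Neither document specifies an arithmetic mean of LNI or a back-transformed mean.

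**The concern.** A geometric mean suits PRNT50 because titers are on the dilution scale: take logs, average, back-transform. With LNI the log has already been taken. Its arithmetic mean is the log10 of the geometric mean neutralisation index, and so is the true counterpart of the PRNT50 GMT. A geometric mean of LNI averages the log of a log10 value and has no such reading.

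The interval has a separate fault. Blaker's exact method is made for discrete parameters such as a binomial proportion. It does not give an interval for the mean of a continuous measure, arithmetic or geometric.

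At stake is the one stated purpose of LNI in this trial, comparison with historical datasets. Protocol 2.2.1.1 cites an LNI of at least 0.7 as the original definition of protective immunity, so readers will look at group LNI summaries with that scale in mind. SAP 2.1 says the Day 57 results will support a manuscript and may inform the design of later trials.

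**Working it through.** **Inputs from the documents.** LNI limit of detection 0.70 and substitute 0.35 (SAP 3.3); 10 vaccine recipients per dose (SAP 5).

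**Assumptions, not in the documents.** Responders share one LNI value r between 1.0 and 3.0; the number of responders k is 2 to 8 of 10; non-responders are set to 0.35.

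**The plan's own figure.** 0.70 / 2 = 0.35, as stated.

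**Formulas.**
- Arithmetic mean: AM = [k·r + (10 − k)·0.35] / 10.
- Geometric mean: GM = exp{[k·ln r + (10 − k)·ln 0.35] / 10}, with ln 0.35 = −1.0498.

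**Worked case, r = 2.0 and k = 5.**
- AM = (10 + 1.75) / 10 = 1.175.
- GM = exp[(5 × 0.6931 − 5 × 1.0498) / 10] = exp(−0.1783) = 0.837.
- Shortfall 0.338.

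**Range of cases.**

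| Responder LNI | Responders of 10 | AM | GM | Shortfall |
|---|---|---|---|---|
| 1.0 | 2 | 0.480 | 0.432 | 0.048 |
| 1.0 | 5 | 0.675 | 0.592 | 0.083 |
| 1.0 | 8 | 0.870 | 0.811 | 0.059 |
| 1.5 | 5 | 0.925 | 0.725 | 0.200 |
| 2.0 | 3 | 0.845 | 0.590 | 0.255 |
| 2.0 | 5 | 1.175 | 0.837 | 0.338 |
| 3.0 | 2 | 0.880 | 0.538 | 0.342 |
| 3.0 | 5 | 1.675 | 1.025 | 0.650 |
| 3.0 | 6 | 1.940 | 1.270 | 0.670 |
| 3.0 | 8 | 2.470 | 1.952 | 0.518 |

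The smallest shortfall in the assumed range is 0.048 (r = 1.0, k = 2). The largest is at r = 3.0, k = 6: AM = (18 + 1.4) / 10 = 1.940; GM = exp[(6 × 1.0986 − 4 × 1.0498) / 10] = exp(0.2392) = 1.270; difference 0.670.

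**Direction.** A geometric mean of positive values never exceeds their arithmetic mean, and 0.35 is the lowest value possible after substitution. In a group that mixes responders and non-responders the shift is therefore always toward 0.35, whatever the responder values are.

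**Where it vanishes or changes character.** With 0 of 10 responders, or 10 of 10 at one common value, AM = GM. If all 10 are detectable and spread evenly from 0.70 to 2.5, AM = 1.600 and GM = 1.487, a smaller gap that involves no substituted value.

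**Dependence on the substitute.** With 5 of 10 responders at 1.5, changing the substitute from 0.35 to 0.10 moves AM from 0.925 to 0.800, but GM from 0.725 to 0.387.

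**Seroconversion.** The substitute 0.35 is below 0.70, so no subject's LNI seroconversion status depends on which mean is used.

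**The case against.** The best defence is that no methods sentence orders a geometric mean of LNI. SAP 9.1 says geometric mean for PRNT50, SAP 9.2 drops the phrase for LNI, the titles of Tables 30 and 31 name GMT and LNI separately, and SAP 6.6 applies the log only as appropriate. A programmer might simply average LNI. This stands as a limit on certainty: the evidence for a geometric mean is SAP 3.3 plus the shared column head, and a double log is not certain to be computed. It does not remove the defect, because the only statistic the SAP names for LNI is a GMT and SAP 9.2 offers nothing in its place.

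It is also fair that the consequences are limited. LNI is exploratory and optional, Listing 14 gives every individual value, and Figures 15 to 18 show the distributions, so either mean can be recovered.

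Three stronger readings are tempting and are not supported:
- **That the group result would fall on the wrong side of the protective level.** With 3 of 10 responders at 2.0 the two means do straddle 0.70 (0.845 against 0.590). That is one assumed case. SAP 3.3 applies 0.70 to individual values, and neither document sets a threshold for a group mean.
- **That the summary is a biased estimate.** The documents define no target parameter for LNI, and how the historical datasets summarised it cannot be seen from them. What can be said is that the geometric mean of LNI is a different quantity, never above mean LNI and harder to interpret.
- **That 0.35 is itself wrong because half the limit was taken on the log scale.** Halving on the index scale would give log10(10^0.70 / 2) = 0.40, a difference of 0.05. Any substitute below the limit is a convention, so this is a preference and not an error.

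**Conclusion.** The point holds as a fault of specification and labelling that would give an unsuitable summary if followed as written. SAP 3.3 and Tables 30 and 31 attach GMT to a log10 measure, while SAP 9.2 leaves the point statistic unnamed and pairs it with an interval that does not apply to a mean.

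The direction is certain for any group whose LNI values differ: the geometric mean is the lower of the two. The size is not known in advance. The range of about 0.05 to 0.67 log10 rests wholly on the assumed responder values and counts and on giving all responders one value. No safety result, PRNT50 result or LNI seroconversion count is affected. It is worth correcting because the repair is cheap and the LNI summary is meant for outside comparison.

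**What to change.** 1. **SAP 3.3:** limit GMT to PRNT50. For LNI, say that values below 0.70 are set to 0.35 for seroconversion and for the mean. Keep 0.35.
2. **SAP 9.2:** state that LNI is summarised by its arithmetic mean with a t-based 95% CI, in place of the Blaker interval. Add that the CI is shown as not estimable when every value in a group equals the substitute. This could well occur in the placebo group, where a t interval would have zero width.
3. **Tables 30 and 31:** give the LNI block its own header (N, Mean LNI, 95% CI) in both tables. Renaming the shared column would mislabel the PRNT50 rows.

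The cost is a few sentences of SAP text, one added header in each of two shells and a small programming change. No new data, assay work or sample is needed.
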